1 BACKGROUND INFORMATION AND RATIONALE

1.1 Introduction

Acute myeloid leukemia (AML) is the second most common pediatric hematologic malignancy with approximately 600 new cases per year among patients under 20 years of age. Although AML accounts for only about 20% of leukemias in children, it is responsible for more than half of pediatric leukemia deaths (1).

All pediatric patients with newly diagnosed AML receive multiple consecutive courses of intensive myelosuppressive chemotherapy aimed to attain complete remission (induction) and to prevent relapse (intensification) (2). Each regimen is followed by a period of prolonged severe neutropenia during which patients are at high risk for infection and hemorrhage. Previous reports have found that 57-80% of febrile neutropenia episodes among pediatric AML patients are compromised by at least one microbiologically documented infection (3, 4) with bacteremia constituting the most prevalent infection (5). These infectious complications remain a major cause of therapy-associated morbidity and mortality in children with AML (6, 7).

Recently published pediatric neutropenia guidelines make no specific recommendations regarding discharge from hospital after chemotherapy for AML because "there are no validated schemas for defining those patients at high-risk of developing complications of fever and neutropenia" (8). As a result, clinicians are left to decide whether to keep a child in the hospital until the neutropenia resolves (on average 35 days) or discharge a child to outpatient management within a few days of chemotherapy completion with instructions to return if symptoms of infection develop. Physicians that elect to observe patients with neutropenia in the hospital do so under the assumption that hospital observation will reduce the risk of serious infection and thereby reduce delays in starting the next course of chemotherapy. There is documented variation in practice across Children's Oncology Group (COG) institutions on inpatient versus outpatient management of neutropenia with approximately 60% of COG institutions reporting a policy to always keep patients hospitalized during severely neutropenic periods and the remaining 40% of hospitals reporting a policy of home management some or all of the time (9, 10). This variation in practice highlights the need for additional data on clinician-centered outcomes to appropriately guide the management of neutropenia in pediatric AML patients.

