1.2 Relevant Literature and Data

The limited literature on the clinical consequences of outpatient versus inpatient management of neutropenia in AML is focused on the experience of adult patients. Adult

patients discharged early to outpatient supportive care consistently had shorter cumulative lengths of stay than inpatients (11-18). Additionally, early discharge of adult AML patients receiving chemotherapy has been associated with fewer and shorter febrile episodes (15, 19), a better response to first line antibiotics, and shorter duration of intravenous antibiotic administration (13, 15, 18, 19). While these adult studies provide some reassurance that outpatient management may be safe and feasible they are limited as most included data from only a single institution, had very small sample sizes, or lacked an appropriate inpatient reference population. Furthermore, it is not appropriate to extrapolate these adult findings to pediatric patients as the risk profile for children may be much different.

The published literature with respect to outpatient management of neutropenia in pediatric AML is limited to a single study of only 13 patients from one hospital, which found similar rates of relapse and mortality for outpatient versus inpatient management of neutropenia (20). In our own preliminary analyses based on administrative resource utilization data from 43 free-standing children's hospitals in the US, we found that patients who were discharged early to outpatient management following AML induction and intensification chemotherapy courses incurred fewer cumulative days of hospitalization, but were frequently readmitted and had higher rates of antibiotic, vasopressor, and supplemental oxygen utilization than patients who remained inpatient during the entirety of their neutropenia. In the absence of clinical data and laboratory confirmation, it is unclear whether these observed increases in resource utilization are an accurate proxy for a greater incidence of infection or more severe infection in the early discharge patients.

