3.4 Study Population

The study population will include all AML and MDS patients who received or will receive chemotherapy starting January 1, 2012 at any of the seventeen participating pediatric institutions across the US. Patients discharged within 3 days after completion of that chemotherapy course will be categorized as 'early discharge' to outpatient management during neutropenia. Patients meeting eligibility criteria for 'early discharge' but remaining in the hospital more than 3 days after completion of that chemotherapy course will be categorized as inpatient management. Patients will be considered early discharge-eligible if there is no evidence of fever, infection or intensive care unit (ICU) level care within \pm 3 days of the last dose of chemotherapy.

3.4.1Aim 1 Inclusion Criteria

- 1) Males or females less than 19 years of age at initial AML/MDS diagnosis.
- 2) Receipt or planned receipt of standard intensive AML frontline chemotherapy any time from January 1, 2012 or after.

3.4.2Aim 1 Exclusion Criteria

- Patients being treated for relapsed AML
- Patients with Acute Promyelocytic Leukemia (APML)
- Patients undergoing stem cell transplant (SCT)
- Patients receiving reduced intensity frontline chemotherapy

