6 STATISTICAL CONSIDERATIONS

6.1 Primary Endpoint

The primary outcomes will include the following two endpoints (ascertained from patient medical records):

1.) Occurrence of post-chemotherapy bacteremia

Identification of bacteremia will begin three days after completion of a chemotherapy course and will continue until recovery of neutrophil count (ANC > $200~\mu L$), or until the start of the next course (for a very small number of patients who begin the next course of chemotherapy prior to count recovery). Bacteremia will be defined as a single positive blood culture for a bacterial pathogen (including Viridans group Streptococci). If the bacterium is an organism considered as a common commensal organism by the National Healthcare Safety Network, two separate positive blood cultures will be required for classification as bacteremia.

2.) Time to the initiation of the next chemotherapy course

Time to next course of chemotherapy will be measured as the number of days from the three days after the completion chemotherapy in a given course until the first day of the next course.

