6.2 Control of Bias and Confounding

This is an observational cohort study, so subjects are not assigned by a process of randomization and are therefore subject to bias. However, analyses of our data will control for potential confounding by various patient- and hospital- level factors. Additionally, there is a possibility of exposure misclassification given that patients who are discharged more than 3 days after chemotherapy completion but well before neutropenia recovery will still be included in the inpatient management group. To account for this imperfect specificity, sensitivity analyses will be performed utilizing a less strict threshold for discharge classification (e.g., 5- or 10 days post-chemotherapy).

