6.3 Statistical Methods

6.3.1 Analysis of Primary Outcomes of Interest

Propensity score analyses will be used to adjust for potential confounding by baseline covariates. First, bivariate analyses will be performed to evaluate relationships between each baseline covariate and neutropenia management strategy as well as each outcome of interest. Next, propensity scores will be derived from the predicted probabilities estimated from logistic regression models of the use of outpatient versus inpatient management during neutropenia conditional on all baseline factors determined to be true confounders (i.e., those associated with both exposure and outcome) and those determined to be potential confounders (i.e., those associated only with the outcome interests). Patients will then be stratified into five groups using quintiles of the estimated propensity score. The distributions of exposure within the quintiles will be examined for sufficient sample sizes and balance. Within each stratum, the patients managed as outpatient and those managed as inpatient will ideally have similar values of the propensity score and likewise the distribution of measured baseline covariates will be comparable between them.

Log-binomial regression will be used to estimate risk ratios with 95% confidence intervals (CI) comparing the incidence of bacteremia following outpatient versus inpatient neutropenia management strategy. Control for confounding will be accomplished through adjustment for propensity score by quintiles as well as any remaining unbalanced patient- or hospital-level confounders.

Generalized linear regression models will be utilized to compare time (in days) from three days after completion of one chemotherapy course to initiation of the next course of chemotherapy by neutropenia management strategy (outpatient versus inpatient). Before model fitting, the normality of the outcome will be assessed. If the normality assumption holds, then traditional linear models (normal distribution with an identity link) will be utilized. If the distribution of time to next course is significantly skewed, then models assuming a gamma or log-normal distribution as appropriate will be used. Again, control for confounding will be accomplished through adjustment for propensity score by quintiles as well as any remaining unbalanced confounders.

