6.4 Sample Size and Power

Assuming 100% capture of eligible patients (waivers of consent obtained from all participating sites), we expect to identify a total of 600 newly diagnosed AML/MDS patients across the seventeen participating centers. Assuming 90% of identified patients will be early discharge eligible, the anticipated study population will be 540 patients. Based on the rates for the individual participating sites, approximately 27% of the study population will be managed as outpatients (n=146) and the remaining will be managed as inpatients (n=394) during neutropenia. Assuming a baseline risk of bacteremia of 60%, the proposed size of the two study arms would provide greater than 80% power to detect a 13% difference in bacteremia rates among patients managed as outpatients versus those that remain hospitalized, with a significance level of 0.05. A 13% difference in bacteremia rates would also be a clinically significant difference. For time to next chemotherapy course, we used a two sample t-test in the power calculation to be conservative (i.e., statistical analysis using a generalized linear model with correct distribution will result in creased power over a t-test). Assuming each patient contributes one treatment course and an average time to next chemotherapy course of 29 days and a standard deviation (SD) of 10 (based on preliminary data), our study will have 85.0% power to detect a difference of 3 days between the two groups, with a significance level of 0.05.

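### The 10-day discharge sensitivity analysis moves the exposure cut-off but not the start of bacteremia counting, so early bacteremia may help decide who counts as inpatient

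*Combined protocol and SAP*

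**What the plan says.** In the primary analysis three clocks meet at day 3.

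- Exposure (section 3.4): children who leave by day 3 after a course are early discharge; eligible children who stay longer are inpatient.
- Eligibility (section 3.4): the child must have "no evidence of fever, infection or intensive care unit (ICU) level care" in the three days either side of the last dose.
- Outcome (section 6.1): "Identification of bacteremia will begin three days after completion of a chemotherapy course", and it runs until neutrophil recovery or the next course.

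Section 6.2 recognises that "patients who are discharged more than 3 days after chemotherapy completion but well before neutropenia recovery" stay in the inpatient group. Its remedy is that "sensitivity analyses will be performed utilizing a less strict threshold for discharge classification (e.g., 5- or 10 days post-chemotherapy". No section moves the eligibility window or the start of counting to the new threshold, or names a landmark or time-dependent method. On adjustment, section 6.3.1 says "Propensity score analyses will be used to adjust for potential confounding by baseline covariates".

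**The concern.** With a 10-day threshold, exposure is still being decided on days 3 to 10, when outcome events already count. A child who becomes bacteremic on day 6 and is kept past day 10 enters as an inpatient event. A child who leaves on day 9 will tend to have been free of bacteremia until then. That lowers the apparent outpatient risk and raises the inpatient risk even if setting makes no difference. Baseline adjustment cannot remove sorting that happens after baseline.

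The check exists to undo dilution from later discharges, and its result will be read as evidence of robustness. If it leans toward outpatient management, a null or protective 10-day result, or agreement with the primary, could reassure wrongly. A harm signal that persisted would still be informative, because the bias runs against it.

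**Working it through.** **1. The plan's own figure.** Section 6.4 claims more than 80% power for a 13-point difference. For 394 at 60% and 146 at 73%, two-sided 0.05, the standard errors are 0.0466 (pooled) and 0.0443 (unpooled). Then (0.13 − 1.96 × 0.0466)/0.0443 = 0.87, which is 80.8% power. The figure reproduces. It does not decide this point, but its inputs are used below.

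**2. Inputs.** From the documents: 540 patients, 27% out by day 3 (section 6.4); "Assuming a baseline risk of bacteremia of 60"% (section 6.4); inpatient stay "until the neutropenia resolves (on average 35 days" (section 1.1). Assumed, because the documents are silent:

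- f: share of the other 73% due to leave, evenly spread over days 3 to 10.
- b: probability that bacteremia before the planned discharge day keeps the child in past day 10.
- End of the risk window: day 28 or day 35, so T = 25 or 32 days after day 3.
- Hazard shape. With x = days since day 3 and c = −ln 0.4 = 0.916, the cumulative hazard H(x) is c·x/T (constant), c·(x/T)² (rising) or c·[1 − (1 − x/T)²] (front-loaded). Each gives 60% risk by the end.

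**3. Formulas, no true effect.**

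- q = average of 1 − exp(−H(x)) over x from 0 to 7
- B = 0.73·f·b·q, the fraction moved to inpatient by bacteremia
- Outpatient risk = [0.6(0.27 + 0.73f) − B] / (0.27 + 0.73f − B)
- Inpatient risk = [0.6 × 0.73(1 − f) + B] / [0.73(1 − f) + B]

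Example (constant hazard, T = 25, f = 20%, b = 1): q = 0.118 and B = 0.146 × 0.118 = 0.0172. Outpatient risk = (0.2496 − 0.0172)/(0.416 − 0.0172) = 0.583. Inpatient risk = (0.3504 + 0.0172)/(0.584 + 0.0172) = 0.611. The difference is −2.9 points, risk ratio 0.953. If b = 0, B = 0 and there is no bias.

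**4. Dilution recovered.** Under a true 13-point harm at home, the hazard is multiplied by ln 0.27/ln 0.40 = 1.43 from discharge onward. Recovered = (as-written − primary)/(reclassified without sorting − primary), as risk differences. For constant hazard, T = 25, f = 20%: primary 10.7, without sorting 12.5, as written 11.3 (b = 0.5) or 10.1 (b = 1). That is 34% recovered, or less than none.

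**5. Results at f = 20%.**

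| Hazard | Window to day | q | Null bias in points, b = 0.5 / 1 | Recovered, b = 0.5 / 1 |
|---|---|---|---|---|
| Rising | 28 | 0.023 | −0.28 / −0.56 | 91% / 81% |
| Rising | 35 | 0.014 | −0.17 / −0.35 | 94% / 89% |
| Constant | 28 | 0.118 | −1.43 / −2.87 | 34% / below 0 |
| Constant | 35 | 0.094 | −1.13 / −2.28 | 52% / 5% |
| Front-loaded | 28 | 0.201 | −2.44 / −4.95 | below 0 / below 0 |
| Front-loaded | 35 | 0.165 | −2.00 / −4.05 | below 0 / below 0 |

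Simulation of the same scenarios agrees to about 0.1 point (0.2–0.7, 1.2–2.9 and 2.0–5.0).

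**6. Scale.** At f = 20% the 10-day split is about 225 against 315, so the 95% CI half-width is 1.96·√(0.24/225 + 0.24/315) = 8.4 points. Under constant hazard a nominally significant outpatient benefit would then appear in 4.5–9.8% of null studies instead of 2.5%. Also under constant hazard: at f = 5–10% the bias is at most 1.6 points; if later discharges cluster on days 3 to 5, 70–89% of the dilution is recovered (f = 20–30%); and at the 5-day threshold, with f = 20% all leaving on days 4–5, the bias is 1.0–1.3 points.

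**The case against.** The strongest reply is that this is one example threshold of a secondary check described in a single sentence, and that the analysts may intend to move the windows with it. That may be so, but the text does not say it, and writing it down is cheap.

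Three further objections stand and limit the point.

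- **Direction is inferred.** No section says that bacteremia delays discharge. The nearest support is that section 3.4 treats infection near the end of chemotherapy as ruling out early-discharge eligibility.
- **Size depends on hazard shape.** With a rising hazard the bias is trivial and most of the dilution is recovered. A reader might infer from the constant-hazard rows that the check recovers little or nothing. The documents give no timing of bacteremia within neutropenia, so they do not support that.
- **A landmark on bacteremia alone can leave similar sorting.** If, by assumption, 30% have fever that keeps them in hospital and carries 1.5 to 2 times the hazard, the landmark's null risk ratio is 0.92–0.97 (−1.7 to −4.3 points). The remedy must therefore carry the plan's other screens forward.

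A reader might also take section 1.2 as evidence that early discharge causes more infection, since early-discharge patients had fewer hospital days "but were frequently readmitted and had higher rates of antibiotic, vasopressor, and supplemental oxygen utilization than patients who remained inpatient". The same section says that it is unclear whether this resource use reflects infection. It shows only which way false reassurance would matter.

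**Conclusion.** The point holds for the 10-day sensitivity analysis as written and, to a smaller degree, the 5-day one. It is conditional: if bacteremia on days 3 to 10 lowers the chance of discharge by day 10, the check is biased toward outpatient management. I am confident of that direction but not of the size, because the documents give neither the number leaving on days 4 to 10, nor how often bacteremia blocks discharge, nor when in neutropenia it occurs. At an assumed 20% share the bias runs from negligible to about 5 points, and the dilution recovered from nearly all to less than none.

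A reader might extend this to the primary comparison. That does not follow: exposure, eligibility and counting all meet at day 3 there. Nor is anything claimed about time to next course. The change should be made because a robustness check should not share a clock with its own outcome, not because a large error has been shown.

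**What to change.** In section 6.2, for each threshold k, add a landmark version:

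- exposure is discharge by day k;
- eligibility requires no bacteremia, other infection or ICU care through day k, with a variant also requiring no fever (temperature records may be less complete for children at home);
- bacteremia is counted from day k.

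Report it beside the primary and as-written results as risk differences. Risk ratios are not comparable: under constant hazard, a true 13-point harm and no misclassification, the landmark ratio is 1.25–1.26 against 1.217, while its difference is 12.7–12.9 points against 13.0. Tabulate discharges on days 4 to 10, and bacteremias before day k by location, so that readers can judge the size. Clone-censor-weighting from day 3 is optional and needs a censoring model.

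State the downsides. Under constant hazard the day-10 landmark loses 1 − exp(−7c/T) = 18–23% of patients with no effect (98–122 of 540), and up to 26% (142) under the 13-point harm, before infection, ICU or fever exclusions. A front-loaded hazard would cost more. At a 20% share (no effect, constant hazard) the CI half-width rises from 8.4 to 9.5–9.7 points. Events before day k, including early ones at home, are not counted. For example, if hazard doubled on days 3 to 10 only in day-3 dischargees, the primary risk ratio would be 1.12–1.15 and the landmark 1.00. It cannot replace the primary.

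The work is a short paragraph and a re-run on admission and culture dates already listed in section 5.1.1. Positive cultures at outside hospitals are listed there only as yes/no, so their dates must be confirmed first, as must the dating of infections and ICU care up to day k.

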6.3 Statistical Methods

6.3.1 Analysis of Primary Outcomes of Interest

Propensity score analyses will be used to adjust for potential confounding by baseline covariates. First, bivariate analyses will be performed to evaluate relationships between each baseline covariate and neutropenia management strategy as well as each outcome of interest. Next, propensity scores will be derived from the predicted probabilities estimated from logistic regression models of the use of outpatient versus inpatient management during neutropenia conditional on all baseline factors determined to be true confounders (i.e., those associated with both exposure and outcome) and those determined to be potential confounders (i.e., those associated only with the outcome interests). Patients will then be stratified into five groups using quintiles of the estimated propensity score. The distributions of exposure within the quintiles will be examined for sufficient sample sizes and balance. Within each stratum, the patients managed as outpatient and those managed as inpatient will ideally have similar values of the propensity score and likewise the distribution of measured baseline covariates will be comparable between them.

Log-binomial regression will be used to estimate risk ratios with 95% confidence intervals (CI) comparing the incidence of bacteremia following outpatient versus inpatient neutropenia management strategy. Control for confounding will be accomplished through adjustment for propensity score by quintiles as well as any remaining unbalanced patient- or hospital-level confounders.

Generalized linear regression models will be utilized to compare time (in days) from three days after completion of one chemotherapy course to initiation of the next course of chemotherapy by neutropenia management strategy (outpatient versus inpatient). Before model fitting, the normality of the outcome will be assessed. If the normality assumption holds, then traditional linear models (normal distribution with an identity link) will be utilized. If the distribution of time to next course is significantly skewed, then models assuming a gamma or log-normal distribution as appropriate will be used. Again, control for confounding will be accomplished through adjustment for propensity score by quintiles as well as any remaining unbalanced confounders.

Although there will be limited power to quantify heterogeneity of effects across strata of covariates, hypothesis-generating subanalyses will be performed to evaluate the potential for effect measure modification (on both absolute and relative scales) by age, race, and insurance status (as a proxy for socioeconomic status) via stratification to inform future studies.

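### Propensity score covariates are chosen by their observed association with the outcome, which can leave out modest confounders unless the later imbalance adjustment also covers covariates that failed the screen

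*Combined protocol and SAP*

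**What the plan says.** The relevant text is in section 6.3.1 (Analysis of Primary Outcomes of Interest).

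- **Screen.** As a first step, "bivariate analyses will be performed to evaluate relationships between each baseline covariate and neutropenia management strategy as well as each outcome of interest".
- **Entry to the score.** The logistic model for outpatient management is fitted "conditional on all baseline factors determined to be true confounders (i.e., those associated with both exposure and outcome"), together with "those determined to be potential confounders (i.e., those associated only with the outcome interests"). Both classes require an association with the outcome. A covariate tied to exposure but showing no outcome association is not admitted.
- **Stratification.** "Patients will then be stratified into five groups using quintiles of the estimated propensity score".
- **Second adjustment.** The bacteremia model uses "adjustment for propensity score by quintiles as well as any remaining unbalanced patient- or hospital-level confounders". The model for time to next course uses "adjustment for propensity score by quintiles as well as any remaining unbalanced confounders".

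The section names no test or cutoff for the screen, no list of covariates for the score, and no balance metric. Section 5.1.1 lists what is abstracted from the chart, not what enters the model. Section 6.2 accepts that the comparison is not randomised and relies on covariate control.

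**The concern.** Preferring outcome-related covariates in a propensity score is sound when the judgement comes from prior knowledge. Here it comes from looking at covariates one at a time in the data to be analysed. A confounder with a modest effect on bacteremia will often show no clear association in a sample of this size, and one masked by another covariate can also be missed. Several omitted confounders acting in the same direction can add up. Outcome data also shape the exposure model, and the planned 95% confidence intervals do not reflect that selection.

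Because covariate control is the main protection against confounding in this comparison, an omitted confounder would bias the risk ratio for bacteremia. The same rule governs the difference in time to next course.

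**Working it through.** **Inputs from section 6.4.** 600 × 0.90 = 540 evaluable patients, 146 outpatient (27%) and 394 inpatient; baseline bacteremia risk 60%; significance level 0.05. As a check on these inputs, the normal-approximation power for 60% against 73% with 146 and 394 patients, two-sided 0.05, is 80.8%. This agrees with the stated figure of more than 80%, which is not in dispute.

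**Inputs assumed, because the documents give none.** The screening cutoff, the number and strength of the confounders, and the balance threshold.

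**1. Chance that one real confounder fails the screen.** For a binary covariate splitting N = 540 into n1 and n0, with outcome risks p1 and p0 and overall risk p = 0.60:

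P(dropped) = 1 − Φ[(|p1 − p0| − 1.96·se0)/se1], where se0 = √{p(1 − p)(1/n1 + 1/n0)} and se1 = √{p1(1 − p1)/n1 + p0(1 − p0)/n0}.

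Example with 50% prevalence and a 5-point effect: n1 = n0 = 270, p1 = 0.625, p0 = 0.575, se0 = 0.0422, se1 = 0.0421. Then (0.05 − 0.0826)/0.0421 = −0.775 and Φ = 0.219, so P(dropped) = 78%.

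| Effect on bacteremia risk | P(dropped), prevalence 50% to 20%, p<0.05 screen |
|---|---|
| 5 points | 78–85% |
| 8 points | 53–68% |
| 10 points | 34–53% |
| 13 points | 13–30% |

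**2. Bias per omitted covariate.** This is roughly effect × imbalance. With an assumed 20-point imbalance between groups, 0.05 × 0.20 = 1.0 point and 0.13 × 0.20 = 2.6 points.

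**3. Simulation, ten confounders among 20 covariates.** No true effect, 540 patients, about 27% outpatient, about 60% risk. Each confounder has OR 1.18 per SD on bacteremia and 1.22 to 1.35 per SD on outpatient management, all in the same direction. Runs used 1,000 datasets unless noted. The narrow reading limits the imbalance step to factors that passed the screen. The broad reading applies it to any measured covariate with a standardised difference above 0.1.

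| Approach | Estimated RR | False-positive rate |
|---|---|---|
| p<0.05 screen, narrow reading | 1.046–1.068 | 10.9–14.9% |
| p<0.05 screen, broad reading | 1.005–1.010 | 4.9–5.6% |
| All 20 covariates in the score | 1.008–1.014 | 4.7–6.0% |

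The ranges span separate runs. At 1,000 datasets, the simulation standard error of a rate near 13% is √(0.13 × 0.87/1000) = 1.1 points. On the narrow reading, adding back only screened-in factors changed nothing (RR 1.056 and 13.7% with or without it). At 60% risk, an RR of 1.046–1.068 is 0.60 × 0.046 = 2.8 to 0.60 × 0.068 = 4.1 points.

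Sensitivity, narrow reading: a p<0.20 screen gave 6.8–7.7% (the 7.7% from 600 datasets), and confounders of mixed direction at p<0.05 gave 7.4%.

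**4. Second simulation, binary confounders, risk-difference scale.** 1,500 datasets per scenario, no true effect. Entries are bias in points. Screen-only is the screened score with no add-back. Imbalance was measured across the whole groups.

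| Scenario | Crude | Screen only | Screen + any unbalanced | Fixed list |
|---|---|---|---|---|
| 6 confounders, 6 points, log-OR 0.5 | 4.1 | 2.0 | 0.05 | 0.3 |
| Same, p<0.20 screen | 4.2 | 1.0 | 0.3 | 0.4 |
| 10 confounders, 5 points, log-OR 0.4 | 4.5 | 2.4 | 0.1 | 0.2 |
| 6 confounders, 10 points, log-OR 0.5 | 6.9 | 1.7 | 0.4 | 0.6 |
| 3 confounders, 5 points, log-OR 0.4 | 1.4 | 0.8 | 0.0 | 0.1 |

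False-positive rates here were milder: 4.9–9.3% for screen only, 4.9–5.8% with the broad add-back, 5.3–5.5% for the fixed list. Against the 13-point difference the study is powered for, the screen-only bias is 0.8/13 = 6% to 2.4/13 = 18%.

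**The case against.** The strongest objection is that the score is only half of the stated adjustment. Both outcome models also take in remaining unbalanced confounders, and the section's stated aim within strata is comparability of the measured baseline covariates, not only of those screened in. If the second step follows that aim, the plan does as well as a fixed list in every scenario above. This stands as far as it goes. But the sentence that sets up the step speaks of confounders, and the same section has just defined both kinds by their association with the outcome. A covariate that failed the screen is neither. That favours the narrow reading without settling it.

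Several stronger readings are tempting, and the documents do not support them:

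- *The plan applies a 5% significance test.* The text speaks of bivariate analyses and of factors determined to be confounders. A test is a natural inference, but no cutoff is given, and a looser one shrinks the problem.
- *The plan does drop true confounders.* It can; whether it does depends on effects the documents do not report.
- *A false-positive rate of 11–15% is a property of the plan.* It belongs to one assumed scenario with ten confounders all pushing the same way, which is close to a worst case.
- *Admitting outcome-only factors, or leaving out exposure-only ones, is a fault.* It is not. The fault lies in learning outcome relevance from the same data.
- *A fixed list would remove the bias.* It would largely reduce bias from measured covariates. Quintiles leave a small remainder, and unmeasured confounding is untouched.

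**Conclusion.** The point holds in a limited form. Section 6.3.1 states a data-driven entry rule that can omit modest confounders at N = 540, and the step that could repair this is worded so that it may not reach them. In the ten-confounder scenario the two readings of that sentence differ materially: false-positive rates of about 11–15% against about 5%, with a risk ratio of about 1.05–1.07 against 1.01 when the truth is 1. With a looser screen or mixed directions the narrow reading gives about 7–8%, and with fewer or differently structured confounders it ranges from no inflation to about 9%.

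These sizes rest on assumed covariate strengths, cutoffs and balance thresholds. They concern bacteremia only; the bias in days for time to next course was not quantified. The direction of the recommendation does not depend on them, since a prespecified list kept the rate near 5% throughout.

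**What to change.** In section 6.3.1:

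1. Replace the screening rule with a list of propensity covariates chosen on subject-matter grounds before outcomes are examined, and enter all of them regardless of p-value.
2. Draw the list from section 5.1.1 items known by three days after chemotherapy completion, when both outcome windows open. Candidates are age, sex, race/ethnicity, AML/MDS subtype and risk class, course and regimen, Down syndrome, central line, mucositis, nutritional status, insurance, calendar year (derivable from course dates) and systemic antimicrobial prophylaxis. Add at least one hospital-level factor, since sections 6.2 and 6.3.1 commit to hospital-level control.
3. Leave out variables believed to affect only the discharge decision. Language and transport access need that judgement made explicitly.
4. Keep the bivariate tables as description.
5. Judge balance by standardised differences within quintiles, with a stated threshold such as 0.1.
6. State that the remaining-imbalance adjustment applies to every listed covariate, for both primary endpoints.

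The cost is plan wording; the patient-level items are already abstracted or derivable. The downside is a slight loss of precision if a listed variable is unrelated to the outcome. In one simulation the spread of the log risk ratio rose from 0.074 to 0.078, about 5% (0.078/0.074 = 1.05).
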